6.5 EXPLORATORY EFFICACY ANALYSES

The analysis population for the efficacy analyses will consist of all patients.

The exploratory efficacy endpoints will be summarized by descriptive statistics based on the following calculations, with clinical response and clinical remission as defined in Sections 3.1.4.2 and 3.1.4.3.

- Proportion of patients with a clinical response
- Proportion of patients with a clinical remission
- Time from clinical remission to loss of clinical remission
- Change from baseline (i.e., either the baseline score in the parent study or the last score prior to initiation of the most recent course of efmarodocokin alfa 60 µg/kg IV Q4W during the extension study, whichever score is the most recent) in PRO2 for patients with CD

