Inclusion of efmarodocokin alfa non-responders will enable the Sponsor to gather more data on the benefit-risk profile of continuing efmarodocokin alfa treatment in patients with active disease. The 8-week induction timepoint in parent study GA39925 was chosen to balance seeing a biological effect of efmarodocokin alfa and minimizing time on placebo for patients randomly allocated to the placebo arm. At this time, the optimal induction time period is not known. In addition, patients may subjectively improve with efmarodocokin alfa in parent study GA39925 but be classified per protocol as non-responders (e.g., decline in stool frequency from 20 to 10 times per day with no change in stool frequency subscore). Therefore, protocol-defined non-responders to efmarodocokin alfa are not actively excluded from Study GA40209. Inclusion of these patients from parent study GA39925 enables a preliminary assessment of the benefit-risk of longer duration of treatment, in particular, for more refractory populations (e.g., anti-TNF inadequate responders). In addition, for more refractory populations, combination therapy is often required to induce response and remission.

For all non-responders in parent study GA39925, Study GA40209 will provide a preliminary assessment of combination therapy strategies with concomitant medications prohibited or not used in parent study GA39925 (e.g., use of steroids for patients not on steroids or use of higher doses of steroids). Furthermore, this study will provide an additional option for patients for whom the benefit-risk of continuing in Study GA40209 may be preferred over pursuing other clinical trials or treatment options (e.g., patients who are subjectively improving but do not meet protocol-defined response criteria).

Vedolizumab Responders

Vedolizumab responders from parent study GA39925 are not excluded should the patient want to switch to efmarodocokin alfa. Those patients also have the option to continue vedolizumab outside of the study. For vedolizumab responders (in particular for those who have not achieved clinical remission), Study GA40209 is a preliminary assessment of the benefit-risk of switching to efmarodocokin alfa.

Placebo Responders

Placebo responders are not excluded should the patient choose to receive efmarodocokin alfa, in particular those patients who have not achieved clinical remission. Inclusion of placebo responders will provide further data on the benefit-risk of treatment with efmarodocokin alfa.

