6.2 SUMMARIES OF CONDUCT OF STUDY

The numbers of patients who enroll, discontinue, or complete the study will be summarized. Reasons for premature study withdrawal will be listed and summarized. Eligibility and other major protocol deviations will be listed and evaluated for their potential effects on the interpretation of study results.

Patients who withdraw from the study, irrespective of final outcome, will be considered as non-responders at analysis. All patients who received efmarodocokin alfa in this study will be pooled for analysis. Further subgroup analysis by dose change during the study or baseline characteristics may be performed if the sample size per subgroup is sufficient.

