6.4 SAFETY ANALYSES

The safety analysis population will consist of all patients who received at least one dose of study drug.

The safety analysis will contribute to the evaluation of the dosing strategy in the enrolled population over the study period, the impact of total cumulative dose received in consecutive months, the impact of intermittent dosing, the impact of total amount of drug received (including dose adjustments) or total number of infusions during the study. Safety will be analyzed through descriptive summaries of adverse events, laboratory test results, and clinical data on the basis of, but not limited to, the following:

- All patients who receive at least one dose of study drug

- Total dose received overall
- Total number of infusions overall
- Total number of consecutive monthly doses
- Maximum total cumulative dose received in consecutive months

All verbatim adverse event terms will be mapped to Medical Dictionary for Regulatory Activities thesaurus terms, and adverse event severity will be graded according to NCI CTCAE v4.0.

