6.6 EXPLORATORY PHARMACOKINETIC ANALYSES

Serum study drug concentrations at selected timepoints will be summarized by descriptive statistics. Some of the covariate effects (e.g. patient demographics or disease status at the time of entry) on exposure will also be evaluated. The relationship between serum concentration and some efficacy or safety endpoints will be explored.

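### Section 6.5's all-patients efficacy set is not reconciled with Section 6.2's pool of drug recipients, so one mixed remission rate could be read as drug efficacy

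*Combined protocol and SAP*

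**What the plan says.** Section 6.5 defines the efficacy set: "The analysis population for the efficacy analyses will consist of all patients". Section 6.2 has three relevant sentences. On pooling: "All patients who received efmarodocokin alfa in this study will be pooled for analysis". On withdrawals: "Patients who withdraw from the study, irrespective of final outcome, will be considered as non-responders at analysis". On subgroups: "Further subgroup analysis by dose change during the study or baseline characteristics may be performed if the sample size per subgroup is sufficient". For safety, Section 6.4 does require dosing: "The safety analysis population will consist of all patients who received at least one dose of study drug".

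Other sections determine who could be in the efficacy set:

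- Section 3.1.2 and Table 2: patients in clinical remission at their last parent-study endoscopy are observed and not treated.
- Table 3 footnote b and Section 3.1.6: the plan foresees patients who reach Week 52 or Week 104 without any dose in this study.
- Sections 3.1.4.2 and 3.1.4.3: remission has no dosing condition, and remission alone satisfies response.
- Table 1: response and remission at Weeks 28, 52, 80 and 104 sit under an objective about the efficacy of efmarodocokin alfa.
- Section 1.3: the study is also meant to inform an intermittent, treat-to-remission strategy, including how long remission lasts off treatment.
- Section 3.1.3 and the opening of Section 6: patients who completed Week 52 before Version 6 need not take part in Year 2. Those who do not are completers, on condition that required safety follow-up was done.

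**The concern.** The plan states a dosing condition where it wants one, in Section 6.4, and omits it in Section 6.5. A patient who enters in remission, is never dosed here and stays well would therefore be a success on both main efficacy proportions if Section 6.5 is applied as written. If Section 6.2's pooling sentence governs instead, that patient is outside the set. The two readings give different denominators and can give different rates.

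A split that would separate these patients is only optional under Section 6.2. Section 6.6 names entry disease status for exposure ("Some of the covariate effects (e.g. patient demographics or disease status at the time of entry) on exposure will also be evaluated"), but Section 6.5 does not name it for efficacy.

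What is at stake is interpretation. Section 1.3 says the results will help decide whether this dosing strategy goes into Phase III. A reader of a single rate could not tell whether it describes patients who started the drug with active disease or also includes off-drug outcomes that followed parent-study treatment.

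**Working it through.** **1. The plan's own figure.** Section 6.1 gives 13.3% to 26.7% for 20% sustained remission in 135 patients. The Wald interval is 0.20 ± 1.96 × √(0.20 × 0.80 / 135) = 0.20 ± 0.0675, or 13.25% to 26.75%. It reproduces. It concerns GA39925 non-responders at entry, not all patients.

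**2. Never-dosed patients in the rate.** Let f be the never-dosed share, r their remission rate, and 20% the treated rate. The 20% is borrowed from Section 6.1; f and r are assumptions, because the documents give no counts.

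Mixed rate = 0.20 + f × (r − 0.20)

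| f | r | Mixed rate |
|---|---|---|
| any | 20% | 20% |
| 5% | 50% | 21.5% |
| 10% | 50% | 23.0% |
| 20% | 50% | 26.0% |
| 20% | 100% | 36.0% |

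Only shares enter the formula, so the result is the same at 320 patients or at the lower enrolment that Section 3.1.1 allows. The 36% joins both extremes.

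**3. The same check by entry status.** Assume 20% enter in remission, a quarter of these are later treated with 20% remission, and the rest are in remission at rate r.

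- Entry remitters: 0.25 × 0.20 + 0.75 × r = 42.5% (r = 50%) or 80% (r = 100%).
- All patients: 0.8 × 0.20 + 0.2 × 0.425 = 24.5%, or 0.8 × 0.20 + 0.2 × 0.80 = 32%.
- Entry non-remitters, and the Section 6.2 pool of recipients: 20%.

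**4. Week 104.** Per 100 patients, assume 40 Year 1 withdrawals, d pre-Version-6 completers who skip Year 2, and one third of the remaining 60 − d in remission. If all had continued, the rate would be 20/100 = 20%. For the last column, assume 40% withdrawal in the 52-week cohort too and that none of it rejoins, so that cohort has d/0.6 patients (25 or 50).

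| d | In remission | Skippers as failures | Only skippers excluded | Whole non-continuing cohort removed |
|---|---|---|---|---|
| 15 | 15 | 15/100 = 15% | 15/85 = 17.6% | 15/75 = 20% |
| 30 | 10 | 10/100 = 10% | 10/70 = 14.3% | 10/50 = 20% |

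Excluding only the completers while keeping that cohort's Year 1 withdrawals as failures pulls the rate down. All inputs to this table are assumed.

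**The case against.** The best defence is that Section 6.5 is explicit and specific to efficacy. The pooling sentence sits under study conduct, just before the line on subgroups, and may only mean that recipients are not split by dose or parent arm. On that reading there is no conflict, and an all-enrolled set suits a treat-to-remission study in which observation is part of the strategy. Durability of remission is listed separately, and subgroups are permitted. This stands in part: the all-patients rate is legitimate and should be kept. But that reading of Section 6.2 is not stated, and if it is right, the rate reported under a drug-efficacy objective includes never-dosed patients.

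A reader might infer that many parent-study placebo or vedolizumab remitters will be credited to the drug. The documents do not support that. Section 1.3 describes these patients as ones who want the drug: "Placebo responders are not excluded should the patient choose to receive efmarodocokin alfa, in particular those patients who have not achieved clinical remission" and "Vedolizumab responders from parent study GA39925 are not excluded should the patient want to switch to efmarodocokin alfa". Never-dosed remitters from those arms are possible, but no number is indicated, and others may have had efmarodocokin alfa in the parent study.

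Two further limits hold. Entry non-remitters still mix parent arms in an uncontrolled study, so their rate is a cleaner description and not a treatment effect. And the missing Week 80/104 rule is not peculiar to Year 2 non-participants: the withdrawal sentence does not cover a missed assessment in a patient who remains enrolled either.

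**Conclusion.** The point holds as an unreconciled analysis set and a mixed rate that does not describe drug efficacy on its own. The documents do not show that the reported rate will be inflated. The shift is zero if never-dosed patients remit at the treated rate and upward if they remit more often; the 21.5% to 36% range rests on assumed shares and a borrowed 20%.

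The weight is moderate. The efficacy endpoints are exploratory and descriptive, there is no hypothesis test, and the safety population is properly defined. The change is worth making because it is cheap and uses data already collected.

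The Week 80/104 gap is secondary and minor. It might be read as covering everyone without Year 2 data, but patients who had not reached Week 52 when Version 6 came in continue to Week 104, and Year 1 withdrawals already count as non-responders. The group meant here is the pre-Version-6 Week 52 completers who finished required safety follow-up and did not join Year 2; the text does not give completer status to those who missed that follow-up.

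**What to change.** **Main change.** State in Sections 6.2 and 6.5 which set governs efficacy, and report the Week 28, 52, 80 and 104 proportions by remission status at entry:

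- Patients not in remission at entry, who start drug at Week 0 under Appendix 1 footnote c, as the drug-efficacy summary.
- Patients in remission at entry as one whole group, by parent-study arm once unblinded. Any split into later-treated and never-treated should be descriptive only: treatment follows loss of remission, so the never-treated are selected for staying well.
- All patients, as the strategy summary.

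**Weeks 80 and 104.** State the number of Year 2 non-participants defined above and the denominator used. If they are excluded, do not show only the version that keeps their cohort's Year 1 withdrawals as failures. Also show the rate with the whole non-continuing cohort removed, and a result with the non-participants counted as non-responders, so that the range is visible. If some of that cohort rejoin, say how its withdrawals are allotted.

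**Cost.** Wording and a few more tables, with no new data; the parent-arm split waits for unblinding. Rates may look less favourable and intervals widen. At 20%, the Wald 95% interval is 15.6% to 24.4% with 320 patients, 15.1% to 24.9% with 256 (80% of 320) and 13.1% to 26.9% with 128 (80% of 160). The entry-remitter group would be imprecise: at 50%, the Wilson interval is 28% to 72% with 16 patients (5% of 320) and 38% to 62% with 64 (20% of 320).

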6.6 EXPLORATORY PHARMACOKINETIC ANALYSES

Serum study drug concentrations at selected timepoints will be summarized by descriptive statistics. Some of the covariate effects (e.g. patient demographics or disease status at the time of entry) on exposure will also be evaluated. The relationship between serum concentration and some efficacy or safety endpoints will be explored.

6.7 EXPLORATORY IMMUNOGENICITY ANALYSES

The immunogenicity analysis population will consist of all patients with at least one postbaseline ADA assessment.

The numbers and proportions of ADA-positive patients and ADA-negative patients at baseline (Study Week 0) (baseline prevalence) and after drug administration (postbaseline incidence) will be summarized. When determining postbaseline incidence, patients are considered to be ADA positive if they are ADA negative or have missing data at baseline but develop an ADA response following study drug exposure (treatment-induced ADA response), or if they are ADA positive at baseline and the titer of one or more postbaseline samples is at least 0.60 titer unit greater than the titer of the baseline sample (treatment-enhanced ADA response). Patients are considered to be ADA negative if they are ADA negative or have missing data at baseline and all

postbaseline samples are negative, or if they are ADA positive at baseline but do not have any postbaseline samples with a titer that is at least 0.60 titer unit greater than the titer of the baseline sample (treatment unaffected).

The relationship between ADA status, safety, PK, and biomarker endpoints will be analyzed and reported via descriptive statistics.

6.8 EXPLORATORY BIOMARKER ANALYSES

The biomarker data may be summarized descriptively.

7. DATA COLLECTION AND MANAGEMENT

7.1 DATA QUALITY ASSURANCE

The Sponsor will be responsible for data management of this study, including quality checking of the data. Data entered manually will be collected via EDC through use of eCRFs. Sites will be responsible for data entry into the EDC system. In the event of discrepant data, the Sponsor will request data clarification from the sites, which the sites will resolve electronically in the EDC system.

The Sponsor will produce an EDC Study Specification document that describes the quality checking to be performed on the data. Central laboratory data and all other electronic data, including endoscopy and ECG data, will be sent directly to the Sponsor, using the Sponsor's standard procedures to handle and process the electronic transfer of these data.

eCRFs and correction documentation will be maintained in the EDC system's audit trail. System backups for data stored by the Sponsor and records retention for the study data will be consistent with the Sponsor's standard procedures.

PRO and clinician-reported outcome (ClinRO) data will be collected through the use of paper questionnaires. The data from the questionnaires will be entered into the EDC system by site staff.

7.2 ELECTRONIC CASE REPORT FORMS

eCRFs are to be completed through use of a Sponsor-designated EDC system. Sites will receive training and have access to a manual for appropriate eCRF completion. eCRFs will be submitted electronically to the Sponsor and should be handled in accordance with instructions from the Sponsor.

All eCRFs should be completed by designated, trained site staff. eCRFs should be reviewed and electronically signed and dated by the investigator or a designee.

At the end of the study, the investigator will receive patient data for his or her site in a readable format on a compact disc that must be kept with the study records. Acknowledgement of receipt of the compact disc is required.

7.3 SOURCE DATA DOCUMENTATION

Study monitors will perform ongoing source data verification and review to confirm that critical protocol data (i.e., source data) entered into the eCRFs by authorized site personnel are accurate, complete, and verifiable from source documents.

Source documents (paper or electronic) are those in which patient data are recorded and documented for the first time. They include, but are not limited to, hospital records, clinical and office charts, laboratory notes, memoranda, patient-reported outcomes, evaluation checklists, pharmacy dispensing records, recorded data from automated instruments, copies of transcriptions that are certified after verification as being accurate and complete, microfiche, photographic negatives, microfilm or magnetic media, X-rays, patient files, and records kept at pharmacies, laboratories, and medico-technical departments involved in a clinical trial.

Before study initiation, the types of source documents that are to be generated will be clearly defined in the Trial Monitoring Plan. This includes any protocol data to be entered directly into the eCRFs (i.e., no prior written or electronic record of the data) and considered source data.

Source documents that are required to verify the validity and completeness of data entered on the eCRFs must not be obliterated or destroyed and must be retained per the policy for retention of records described in Section [7.5](#).

To facilitate source data verification and review, the investigators and institutions must provide the Sponsor direct access to applicable source documents and reports for trial-related monitoring, Sponsor audits, and IRB/EC review. The study site must also allow inspection by applicable health authorities.

7.4 USE OF COMPUTERIZED SYSTEMS

When clinical observations are entered directly into a study site's computerized medical record system (i.e., in lieu of original hardcopy records), the electronic record can serve as the source document if the system has been validated in accordance with health authority requirements pertaining to computerized systems used in clinical research. An acceptable computerized data collection system allows preservation of the original entry of data. If original data are modified, the system should maintain a viewable audit trail that shows the original data as well as the reason for the change, name of the person making the change, and date of the change.

7.5 RETENTION OF RECORDS

Records and documents pertaining to the conduct of this study and the distribution of IMP, including eCRFs, paper PRO and ClinRO data (if applicable), Informed Consent Forms, laboratory test results, and medication inventory records, must be retained by the Principal Investigator for 15 years after completion or discontinuation of the study or for the length of time required by relevant national or local health authorities, whichever is longer. After that period of time, the documents may be destroyed, subject to local regulations.

No records may be disposed of without the written approval of the Sponsor. Written notification should be provided to the Sponsor prior to transferring any records to another party or moving them to another location.

The Sponsor will retain study data for 25 years after the final Clinical Study Report has been completed or for the length of time required by relevant national or local health authorities, whichever is longer.

8. ETHICAL CONSIDERATIONS

8.1 COMPLIANCE WITH LAWS AND REGULATIONS

This study will be conducted in full conformance with the ICH E6 guideline for Good Clinical Practice and the principles of the Declaration of Helsinki, or the applicable laws and regulations of the country in which the research is conducted, whichever affords the greater protection to the individual. The study will comply with the requirements of the ICH E2A guideline (Clinical Safety Data Management: Definitions and Standards for Expedited Reporting). Studies conducted in the United States or under a U.S. Investigational New Drug (IND) Application will comply with U.S. FDA regulations and applicable local, state, and federal laws. Studies conducted in the European Union or European Economic Area will comply with the E.U. Clinical Trial Directive (2001/20/EC), the General Data Protection Regulation (2016/679), and applicable local, regional, and national laws.

8.2 INFORMED CONSENT

The Sponsor's sample Informed Consent Form (and ancillary sample Informed Consent Forms such as a Child's Informed Assent Form or Mobile Nursing Informed Consent Form, if applicable) will be provided to each site. If applicable, it will be provided in a certified translation of the local language. The Sponsor or its designee must review and approve any proposed deviations from the Sponsor's sample Informed Consent Forms or any alternate consent forms proposed by the site (collectively, the "Consent Forms") before IRB/EC submission. The final IRB/EC-approved Consent Forms must be provided to the Sponsor for health authority submission purposes according to local requirements.

If applicable, the Informed Consent Form will contain separate sections for any optional procedures. The investigator or authorized designee will explain to each patient the objectives, methods, and potential risks associated with each optional procedure. A separate, specific signature will be required to document a patient's agreement to participate in optional procedures. Patients who decline to participate will not provide a separate signature.

After discussion of the study with the investigator, patients must be given ample time to review what has been discussed and have their questions answered prior to signing Consent Forms. Patients must be told that they are free to refuse to participate and may withdraw their consent at any time for any reason without penalty or loss of benefits to which they are otherwise entitled. The Consent Forms must be signed and dated by the patient before his or her participation in the study. The case history or clinical records for each patient shall document the informed consent process and that written informed consent was obtained prior to participation in the study.

The Consent Forms should be revised whenever there are changes to study procedures or when new information becomes available that may affect the willingness of the patient to participate. The final revised IRB/EC-approved Consent Forms must be provided to the Sponsor for health authority submission purposes.

Patients must be re-consented to the most current version of the Consent Forms (or to a significant new information/findings addendum in accordance with applicable laws and IRB/EC policy) during their participation in the study. For any updated or revised Consent Forms, the case history or clinical records for each patient shall document the informed consent process and that written informed consent was obtained using the updated/revised Consent Forms for continued participation in the study.

A copy of each signed Consent Form must be provided to the patient. All signed and dated Consent Forms must remain in each patient's study file or in the site file and must be available for verification by study monitors at any time.

For sites in the United States, each Consent Form may also include patient authorization to allow use and disclosure of personal health information in compliance with the U.S. Health Insurance Portability and Accountability Act (HIPAA) of 1996. If the site utilizes a separate Authorization Form for patient authorization for use and disclosure of personal health information under the HIPAA regulations, the review, approval, and other processes outlined above apply except that IRB review and approval may not be required per study site policies.

